5.2.1 Constraint Induced Language Therapy (CILT)

Participants will begin 10 sessions of mCILT+ tDCS (or mCILT+sham tDCS) between 2 – 30 days after baseline. Each mCILT session will last 1 to 1.5 hours, during the first 20 minutes of which mCILT will be paired with active or sham tDCS.

The progression of mCILT during therapy will go as follows: Treatment begins with single noun requests, with cuing as needed until the subject performs $\geq 80\%$ accuracy over two trials of 64 (32 treated, and 32 untreated) items with minimum assistance, at which point the action words will be added and the response demand increases to object + action phrases; cuing will be increased and task demands decreased if accuracy falls below 50% until it returns to 75% with minimum assistance. Treatment will progress using these criteria: high then low frequency nouns, verbs, agent noun + verb, and then to sentences of increased length and complexity. Throughout the course of a CILT treatment, the difficulty of each stage of therapy will be scaled to individual participant performance, such that participants' language abilities can be behaviorally "shaped" in a sequential manner to ensure a low rate of failure and a gradual increase of difficulty as improvements are made and new skills are retained. The main communication goals of mCILT are to enhance accuracy, speed, and grammatical complexity of participants' speech.

Note that we will use a modified version of the CILT (mCILT). The modification of CILT includes semantically related noun-verb pairs, a modification that may be better suited to address syntactic structure. We will use a specially designed barrier with a whole cut out that will allow for the tDCS machine to be passed through and monitored by the administrator, but still block the view between participant & researcher. The administrator will be trained not to respond to the nonverbal communication. Participants may use writing as a strategy for self-cuing, if helpful. In these cases, the administrator will provide them with a piece of paper and writing utensil while reminding the participant that they are still required to provide a spoken response to achieve the objective of obtaining a matching card.

All sessions will be digitally video/audio recorded for offline scoring (this will ensure data quality and also allow for additional metrics such as assessing latency to respond)."

5.3 Storage

The tDCS unit will be stored in a locked room in Goddard Labs in which the lab's devices are stored. Only the PI and other members of his research team have keys to this room. When not in use, the unit will be enclosed in a special, dedicated storage container that will be marked

CONFIDENTIAL

with a statement that the enclosed unit is not to be used for clinical purposes. Additionally, the unit itself will be clearly marked with a statement indicating that it is an investigational instrument only.

5.4 *Blinding*

tDCS units have a built in blinding feature via the use of assigned codes which will run specific device parameters.

A master excel file of subjects assignments will be kept by the un-blinded study coordinator. When a subject is randomized, the research team will receive a code to enter into the tDCS unit prior to stimulation. This code will run either a real or sham session. The blinding may be broken in the case of an emergency. To request un-blinding the PI will be informed of the reason for un-blinding and if in agreement will allow the coordinator to tell the researcher what the code means.

5.5 Administration and Accountability

All stimulation sessions will be logged on a daily stimulation summary sheet. These logs will be kept with the subject's data in a secure location in the lab space. This log will include the date of stimulation, the individual administering tDCS, blinding code used, and any notes regarding the session.

5.6 Subject Compliance Monitoring

Noncompliance with regard to the randomized intervention could occur if participants miss therapy sessions or if the wrong code is entered into the tDCS device. To minimize noncompliance due to missed therapy sessions, participants who miss up to 3 sessions will be allowed to make up missed sessions the following week. To avoid error in code entry, researchers will be asked to record the code used in each administration of tDCS in the daily log.

6 Study Procedures

6.1 Enrollment & Screening

The screening visit will consist of:

- Informed Consent + HIPAA
- Review of Inclusion/Exclusion Criteria
- Review of MRI Critiera
- Review of demographics / medical history
- Payment paperwork

The anticipated length of this visit is 30 minutes to 1 hour; depending on questions asked during the consent process and responses to screening questions.

Participants will be asked to stop any other speech or language therapies during the course of their study participation.

6.2 Study Intervention Phase

6.2.1 Visit 1 (Baseline MRI)

Subjects will undergo an MRI scan on a 3T Siemens unit; no contrast will be administered.

The anticipated time of this visit is 1 hour.

CONFIDENTIAL

This material is the property of the University of Pennsylvania.

Depending on patient's schedule / fatigue levels, MRI visits may be combined with another baseline visit or screening.

6.2.2 Visit 2 (Baseline 1)

Subjects will undergo language testing to characterize their impairment:

- Western Aphasia Battery
- Pyramids and Palm Trees
- Philadelphia Repetition Test
- Non-Word Repetition Test
- CILT Baseline Assessment
- Linguistic test for reception of grammar
- Spontaneous Speech – Story telling
- Apraxia Measure – DDK
- National Alzheimer's Center Cohort Tests for FTD
- Communication Confidence Rating Scale for Aphasia

Testing is anticipated to take about 3 hours; however, if the testing length too long for the participant it is possible to split the visit in two. Participants must begin treatment phase of study within 4 weeks of completed baseline testing.

6.2.3 Visit 3 (Baseline 2)

Subjects will repeat full language battery from Visit 2 for reliability.

Testing is anticipated to take about 3 hours; however if the session is too long for the participant it is possible to split the visit in two.

6.3 Phase 2 of the Study (Visits 4-13)

In the treatment phase of the study there will be 10 daily (Monday-Friday) tDCS sessions over 2 consecutive weeks in which 20 minutes of 1.5mA stimulation will be delivered to the left frontotemporal lobe (F7). During stimulation, a 60-90 minute session of mCILT will be completed. The total anticipated time of these visits is about 60-90 minutes.

6.4 Follow Up Phase of the Study

6.4.1 Visit 14 (Immediate Follow-up)

All language assessments performed at baseline will be re-administered at follow-up to assess language function.

Testing is anticipated to take about 3 hours; however if the session is too long for the participant it is possible to split the visit in two.

6.4.2 Visit 15 (MRI Follow-up)

Subjects will undergo an MRI on a 3T Siemens unit; no contrast will be administered.

The anticipated time of this visit is 1 hour.

Depending on patient's schedule / fatigue levels, MRI visits may be combined with follow-up language testing.

CONFIDENTIAL

6.4.3 Visit 16 (6 week Follow-up)

All language assessments performed at baseline will be re-administered at follow-up to assess language function.

Testing is anticipated to take about 3 hours; however if the session is too long for the participant it is possible to split the visit in two.

6.4.4 Visit 17 (12 week Follow-up)

All language assessments performed at baseline will be re-administered at follow-up to assess language function.

Testing is anticipated to take about 3 hours; however if the session is too long for the participant it is possible to split the visit in two.

6.4.5 Visit 18 (12 week Follow-up MRI)

Subjects will undergo an MRI scan on a 3T Siemens unit; no contrast will be administered.

The anticipated time of this visit is 1 hour.

Depending on patient's schedule / fatigue levels, MRI visits may be combined with follow-up language testing.

6.4.6 Visits 19-35 (Crossover)

Participants will crossover into the second half of the study after the 12 week follow-up. Visits 18 & 19 will serve as Baseline and then all study procedures will exactly match the first half of the study. The crossover will include an additional follow-up visit at 24 weeks.

6.5 Subject Withdrawal

Subjects are free to withdraw from the study at any time if they no longer wish to participate. Additionally, participants may be withdrawn from the study prior to the expected completion date for a number of reasons:

- 1) Any adverse outcome or event which may represent a possible health risk to the participant
- 2) Failure of the participant to adhere to protocol requirements
- 3) Worsening of language abilities, or worsening cognition or mood.
- 4) Change of PPA diagnosis

Abrupt discontinuation of tDCS is not associated with rebound effects or other adverse outcomes, so no alternative treatment or transitional therapy will be required if participants discontinue the protocol.

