3.2 Study Endpoints

3.2.1 Primary Study Endpoints

The primary endpoint will be overall change in WAB-AQ between the first baseline visit and the 12 week follow-up (real tDCS compared to sham tDCS).

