6.5.1 Data Collection and Follow-up for Withdrawn Subjects

Should participants wish to withdraw from the study entirely, attempts will be made to seek permission to obtain survival data on such patients throughout the protocol defined follow-up

CONFIDENTIAL

This material is the property of the University of Pennsylvania.

period. It will be a high priority to try to obtain at least survival data on all patients lost to follow-up.

A number of attempts will be made to contact a participants by various means before he or she will be considered lost to follow-up. These methods will consist of three or more of phone calls to participant, followed by a phone call to their caregiver if possible, followed by a certified letter. Should all of these efforts fail to elicit a response the patient will be considered lost to follow-up.

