6.6 Early Termination Visits

All subjects that decide to leave the study early or are asked to by the investigator will be strongly encouraged to continue follow-up visits, but early termination visits are not planned.

7 Study Evaluations and Measurements

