7.6 Efficacy Evaluations

No interim analyses for efficacy are planned, as previous work suggests that the maximal benefit is likely to be obtained at the 12 week endpoint and there is no additional risk to the subject after the tDCS is completed.

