8.5 Subject Population(s) for Analysis

The population that will be subject to analysis will be the full randomized with crossover population. Subjects that are non-compliant with treatment/crossover will be encouraged to continue with follow-up and these measurements will be enter into analysis.

9 Safety and Adverse Events

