9.7 Stopping Rules

The trial maybe stopped for safety concerns or poor study performance, including failure to recruit and/or retain subjects. Subjects who report significant discomfort from tDCS, or worsening of language or cognition during tDCS will remain in the study with treatment discontinuation. Two sources of information about short-term adverse effects of tDCS on language function will be available. First, subjects and family will be asked if they see evidence of deterioration in language or other faculties each day they return for tDCS. Second, the researcher administering the mCILT will see the subject during each treatment session. S/he will be instructed to inform the PI if s/he observes a clinically significant worsening in language function. If the mCILT administrator is concerned, the WAB will be repeated. If this supports a decline from baseline (operationally defined as more than 5 points below baseline), the adverse effect will be reported and the subject will be withdrawn from treatment. In order to support the intention-to-treat analysis, all such subjects will be strongly encouraged to continue follow-up.

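### Section 6.5 allows removal from the study for worsening language, so some week-12 WAB-AQ scores can be missing because of the outcome itself; aligning it with 9.7 is a cheap, low-priority fix

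*Combined protocol and SAP*

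**What the plan says.** All references are to the combined protocol and SAP.

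- **6.5** gives four reasons, besides the participant's own choice, for which someone may be withdrawn from the study. The third is "Worsening of language abilities, or worsening cognition or mood". It is discretionary and states no amount of decline, no instrument and no time window.
- **9.7** says that subjects who report "worsening of language or cognition during tDCS will remain in the study with treatment discontinuation". If a repeat WAB is more than 5 points below baseline, the subject is withdrawn from treatment. Follow-up is then encouraged, with intention-to-treat given as the reason.
- **6.6** covers people who leave early, including those the investigator asks to leave. They "will be strongly encouraged to continue follow-up visits, but early termination visits are not planned".
- **8.5** analyses everyone randomized and adds: "Subjects that are non-compliant with treatment/crossover will be encouraged to continue with follow-up and these measurements will be enter into analysis".
- **8.4.1** specifies a linear mixed model with a random intercept and states no missing-data assumption.
- **3.2.1** defines the primary endpoint as "overall change in WAB-AQ between the first baseline visit and the 12 week follow-up", real against sham.
- **6.4.6** says "Participants will crossover into the second half of the study after the 12 week follow-up". Sections 3.1.5 and 12.3 say that every participant crosses over and at some point receives real stimulation.

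**The concern.** PPA is progressive, and participation lasts about 12 months (4.4). Decline in language is therefore expected, and it is what WAB-AQ measures. Reason 3 ties leaving the study to the primary outcome.

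During the two 2-week stimulation blocks, 6.5 and 9.7 give different instructions for the same event. In the follow-up intervals, which make up most of participation, 9.7 does not apply and 6.5 is the only rule. A participant removed there may have no week-12 score, and one removed in period 1 may supply no within-person comparison.

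If real tDCS slows decline, more of these removals fall on sham. The worst sham outcomes then go missing and the estimated benefit shrinks.

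**Working it through.** **The rules by time of worsening**

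| When | 6.5 | 9.7 | Follow-up |
|---|---|---|---|
| During a stimulation block | May leave the study | Stays in the study, treatment stops, threshold of more than 5 points | Encouraged (6.6, 9.7) |
| Between and after blocks | May leave the study | Silent | Encouraged (6.6) |

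**Figures in the plan.** None describes removal for worsening. The nearest is attrition in 8.3: 15% historically, 25% planned, 31 enrolled per variant group for 25 needed. Dividing by the retained fraction gives 25/0.75 = 33.3, or 34; the stated 31 matches 25 x 1.25 = 31.25. That is a separate matter. It shows only that there is little slack: 31 x 0.75 = 23.25, below 25.

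**Assumed inputs.** The documents give no effect size and no SD, so these are assumptions:
- Change from period baseline at time fraction t (2/14, 8/14, 1) = t x (drift + benefit if real + subject slope + subject-by-period slope) + residual.
- Slope SDs of 2, 3 or 4 each and residual SD 3. The 12-week SD runs from √(4 + 4 + 9) = 4.1 to √(16 + 16 + 9) = 6.4.
- (Drift, benefit) pairs: (-2, 2), (-4, 3), (-3, 5), (-4, 5).
- Benefit grows to week 12, because 7.6 says "previous work suggests that the maximal benefit is likely to be obtained at the 12 week endpoint".
- Trigger: a change below -5 at any visit (the 9.7 threshold). The probability of removal is set so that 15% or 25% are removed in total, which assigns all attrition to reason 3.
- Maximum-likelihood fit with a random subject intercept, period-by-visit and treatment-by-visit effects; 400,000 participants per run.

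Attenuation = 100 x (1 - estimated benefit / true benefit) at week 12.

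**Results when the triggering score is in the data**

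| | 15% removed | 25% removed |
|---|---|---|
| All later visits lost | 0.4-1.5% | 0.7-3.0% |
| Half attend the rest of that period, no period 2 if removed in period 1 | 0.0-0.8% | 0.0-1.3% |
| All later visits lost, full benefit already at the immediate visit | 0.8-3.3% | 1.4-6.3% |
| Increase in standard error | 4-6% | 7-13% |

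- Sham accounts for 59-83% of removals.
- With no true benefit, the estimate is -0.011 to +0.018 points.
- In the first row the loss is 0.01-0.13 points. The standard error with full data at n = 31 is 0.93-1.29, so the largest loss is at most 0.13/0.93 = 0.14 of a standard error.
- Period-1 removals per group of 31: 7.7-8.0% gives 2.4-2.5 people; 13.2-13.9% gives 4.1-4.3.

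**Check on the standard error.** Losing 15% or 25% of participants outright would raise it by 1/√0.85 - 1 = 8.5% or 1/√0.75 - 1 = 15.5%. The simulated rises are smaller because earlier visits are kept. They stem from attrition that 8.3 already anticipates and are not an extra cost on top of it.

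**The case against.** The strongest reply is that the plan already covers most of this. Section 6.6 names the group in question, and no trial can compel attendance. Section 9.7 retains those who worsen during stimulation and does set a threshold, so the absence of one is true of 6.5 only. Section 8.5 analyses everyone randomized, and a mixed model uses partial data. All of this stands, and it is why the point is low priority. It does not remove the conflict between 6.5 and 9.7, or the lack of any stay-in-study rule outside the stimulation blocks.

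Three stronger readings are tempting, and the documents do not support them.

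- **A loss of around 10%.** If the triggering score is left out of the data, the same simulation gives 3.0-12.8%. But about half of the simulated removals are first triggered at the week-12 visit, so that variant discards endpoint values already obtained. Nothing in 6.4.4 or 10.2 suggests that recorded scores would be dropped. Decline noticed between visits could go unrecorded, but the simulation does not model that and the documents give no rate. Likewise, a complete-pairs calculation gives 1.9-2.8 for a true benefit of 3, but 8.4.1 does not plan a complete-pairs analysis.
- **Removed participants forfeit the crossover.** The default in 3.1.5 and 12.3 is that everyone crosses over. Those sections do not address withdrawn participants, so one clarifying sentence is reasonable, but the gap is small.
- **The trial's conclusion is at risk.** The bias is toward no effect and vanishes when there is no benefit, so it cannot create a false positive.

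**Conclusion.** The point holds as a cheap, low-priority improvement. Reason 3 in 6.5 permits removal from the study for decline in the domain of the primary outcome. It contradicts 9.7 during stimulation and stands alone outside it.

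With benefit growing to week 12 and the triggering score recorded, attenuation is about 0.4-3.0% and the standard error rises about 4-13%. Within that scenario these are upper limits: they charge all attrition to a discretionary reason and suppose that 6.6 retains nobody. If the full benefit were present from the immediate visit, the attenuation could reach 6.3%.

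Drift, SD, benefit and trigger are all assumed. The fitted model resembles the 8.4.1 model but is not identical to it, since 8.4.1 lists sequence, period, treatment and treatment-by-period. The direction of the bias is firmer than its size.

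**What to change.** - **In 6.5**, make reason 3 a reason to stop the current stimulation block, not to leave the study, using the 9.7 threshold for language. Leave removal from the study for worsening to reason 1 (health risk), which still covers mood or cognition that endangers the participant, or to the participant's choice. Reasons 2 and 4 are unchanged.
- **State that the remaining WAB-AQ visits stay scheduled and are analysed**, at minimum week 12 of each period. Tele-assessment (3.1.4) and split visits (3.1, Figure 1 footnote) are already allowed.
- **State that the participant remains eligible for the crossover**, in line with 3.1.5 and 12.3, subject to the investigator's safety judgement and the participant's agreement. This sentence matters because a stop rule read as cancelling period-2 stimulation would itself dilute the effect. On the same assumptions the dilution is 4.7-6.3% at 15% and 8.1-10.7% at 25%, even with every visit kept.

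The cost is protocol wording, slightly less investigator discretion, and more assessments in declining participants, who may refuse. At most that is about 31 x 0.15 = 4.7 to 31 x 0.25 = 7.8 people per variant group. The gain depends on how many of them attend.

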6.5.1 Data Collection and Follow-up for Withdrawn Subjects

Should participants wish to withdraw from the study entirely, attempts will be made to seek permission to obtain survival data on such patients throughout the protocol defined follow-up

CONFIDENTIAL

This material is the property of the University of Pennsylvania.

period. It will be a high priority to try to obtain at least survival data on all patients lost to follow-up.

A number of attempts will be made to contact a participants by various means before he or she will be considered lost to follow-up. These methods will consist of three or more of phone calls to participant, followed by a phone call to their caregiver if possible, followed by a certified letter. Should all of these efforts fail to elicit a response the patient will be considered lost to follow-up.

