3.1.4 Follow up Phase

There will be an immediate, 6-week and 12-week follow-up following both the initial component. The crossover component will have an additional 24 week follow-up. The full language assessment will be repeated at each follow-up. Subjects will also be asked to complete an MRI scan at the immediate and 12 week follow-ups. Depending on the patients stamina, language assessments may take three visits.

The follow-up visit may be conducted via tele-assessment.

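### For full withdrawals and losses, section 6.5.1 names only survival data; no section asks someone who declines the full battery for the 12-week WAB-AQ alone

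*Combined protocol and SAP*

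**What the plan says.** All references are to the combined protocol and SAP.

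- **Primary endpoint (3.2.1):** "The primary endpoint will be overall change in WAB-AQ between the first baseline visit and the 12 week follow-up", real against sham. Section 8.1 repeats it.
- **Full withdrawal (6.5.1):** "Should participants wish to withdraw from the study entirely, attempts will be made to seek permission to obtain survival data on such patients". No other item is requested.
- **Lost to follow-up (6.5.1):** "It will be a high priority to try to obtain at least survival data on all patients lost to follow-up". A person is declared lost only after repeated calls, a call to the caregiver and a certified letter.
- **Leaving early (6.6):** "All subjects that decide to leave the study early or are asked to by the investigator will be strongly encouraged to continue follow-up visits". The same sentence then rules out a separate assessment at departure: "but early termination visits are not planned".
- **Analysis population (8.5):** "Subjects that are non-compliant with treatment/crossover will be encouraged to continue with follow-up and these measurements will be enter into analysis".
- **Treatment discontinued for worsening (9.7):** "In order to support the intention-to-treat analysis, all such subjects will be strongly encouraged to continue follow-up".
- **Follow-up burden (6.4.1 to 6.4.4):** each language visit repeats the baseline assessments and takes about 3 hours. It may be split.
- **Remote and home options:** section 3.1.4 says "The follow-up visit may be conducted via tele-assessment". Section 4.5 allows visits without tDCS at home where that is more convenient. Its home-visit conditions are a distance limit and the PI's discretion.

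**The concern.** The fallback item does not match the outcome. Survival appears in none of the primary, secondary or safety endpoints (3.2, 8.1, 8.2), and no analysis in 8.4 names it. The item that matters for a person who is leaving is the 12-week WAB-AQ, and 6.5.1 does not mention it.

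The protocol describes two requests to a leaver: keep attending the scheduled visits, or allow survival to be checked. It sets out no intermediate request for someone who is willing to give the primary outcome but not the whole battery.

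This matters more here than in many trials because 6.5 lists worsening language, cognition or mood as a reason for withdrawal from the study. The missing WAB-AQ values may therefore depend on the outcome itself. Section 8.4.1 states no missing-data assumption and no sensitivity analysis, so the plan names no other safeguard. The intention-to-treat aim in 9.7 depends on having these values.

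**Working it through.** **1. The sections side by side**

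| Situation | What is asked for | WAB-AQ obtained? |
|---|---|---|
| Off treatment or non-compliant, still attending (8.5, 9.7) | Scheduled follow-up | Yes, and entered in the analysis |
| Leaves early, accepts visits (6.6) | Scheduled follow-up | Yes |
| Leaves early, declines the full battery | Nothing specified | Not requested alone |
| Withdraws entirely (6.5.1) | Survival data, with permission | Not requested |
| Cannot be reached (6.5.1) | Survival data | Cannot be obtained |

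The gap is in rows three and four.

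**2. The plan's own figure**

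Section 8.3 gives 25 adequate per variant group, 25% anticipated attrition (15% historically) and 31 enrolled per group. The 31 agrees with 25 × 1.25 = 31.25. Dividing instead gives 25 / 0.75 = 33.3, so 34. That difference is a separate matter, but it explains why 31 falls short of 25 at the plan's own attrition rate.

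**3. How many remain if no leaver gives a 12-week value**

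- At 25%: 31 × 0.25 = 7.75 leave and 31 × 0.75 = 23.25 remain.
- At 15%: 31 × 0.15 = 4.65 leave and 31 × 0.85 = 26.35 remain.
- Break-even: (31 − 25) / 31 = 19.4%. Below that loss the group stays at 25 or more.

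**4. Recovery needed at 25% attrition**

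25 − 23.25 = 1.75 people per variant, and 1.75 / 7.75 = 22.6% of leavers, about a quarter.

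**5. What this means for power**

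The plan gives no effect size or SD, so I assumed a two-sided paired t-test within a variant group at alpha 0.05. I solved for the standardised effect that gives 80% power at n = 25. The result is 0.584. The normal approximation is (1.960 + 0.842) / √25 = 0.560. Evaluable n = 31 × (1 − attrition × (1 − share recovered)).

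| Attrition | Leavers recovered | Evaluable n | Power |
|---|---|---|---|
| 25% | none | 23.25 | 0.77 |
| 25% | one quarter | 25.19 | 0.80 |
| 25% | one half | 27.12 | 0.83 |
| 25% | all | 31 | 0.88 |
| 15% | none | 26.35 | 0.82 |
| 15% | one half | 28.68 | 0.86 |

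The recovery shares are assumptions; the documents give none. The rows with no recovery are worst cases. They give the encouragement in 6.6, 8.5 and 9.7 no credit, and they treat every leaver as having no 12-week value in either period.

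**The case against.** The strongest reply is that the protocol already does most of what is wanted. Leavers are strongly encouraged to attend visits that include the WAB, and 8.5 puts data collected after non-compliance into the analysis. Section 9.7 does the same for people who worsen on treatment, the group of most concern. Visits can be split, done remotely or held at home, and 12.2 lets a subject stop testing at any time, so a partial battery is already possible. All of this stands. What is missing is an explicit request that puts the WAB first.

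Four stronger readings are tempting and are not supported:

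- **That the primary outcome is lost for everyone who leaves.** Sections 6.6, 8.5 and 9.7 contradict this. The gap concerns people who withdraw entirely or decline the full visit.
- **That the plan ranks survival above WAB-AQ, or spends its retention effort on survival.** The wording in 6.5.1 sets a minimum. The contact steps come before anyone is declared lost, so they serve retention in general.
- **That a bias in the real-sham difference can be calculated.** The documents give neither the difference in loss between real and sham courses nor the deficit among leavers. Multiplying the two would also describe completers in separate parallel groups, not a within-person crossover contrast from a mixed model.
- **That one WAB on the day of leaving would replace the endpoint.** The endpoint is fixed at 12 weeks. No analysis says how to use an exit score, and 6.6 plans no such visit.

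Two further limits apply. People who cannot be reached cannot be tested, and those who withdraw entirely must agree. Vital status also has some use, since a death is a serious adverse event under 9.1.2. That is a reason to keep it as the last step.

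**Conclusion.** The point holds as a specific gap in the withdrawal rules. Section 6.5.1 names only survival for full withdrawals and losses, and nothing asks a person who declines the battery for the primary outcome alone. Because worsening language can lead to withdrawal, the values missed may be related to the outcome.

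The size is modest and can only be bounded. At 25% attrition with nothing recovered, a variant group ends at about 23 against the 25 called adequate, and power is about 0.77 instead of 0.80 under the assumed paired test. Recovering about a quarter of leavers closes that. At the historical 15% about 26 remain and there is no shortfall. The true loss should be smaller than the bound, because someone who leaves after Visit 17 has already given a period-1 value that the mixed model can use. A single period does, however, carry less information on the within-person contrast than a pair.

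The better argument for the change is protection of the intention-to-treat comparison at low cost. The size of any bias is not known from the documents.

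**What to change.** 1. In 6.5.1 and 6.6, name the 12-week WAB-AQ of the current period as the priority item for anyone leaving.
2. Ask first for the full follow-up visit. If it is declined, ask for consent to a WAB-only assessment at that same time point, by tele-assessment (3.1.4) or at home (4.5).
3. Ask for vital status only after that.
4. Record the reason for leaving and the mode of assessment, so that outcome-related loss and remote scores can be examined.
5. Reconcile 6.5, which lists worsening among the grounds for withdrawal from the study, with 9.7, which keeps subjects who worsen during tDCS in the study with treatment discontinued. The two lead to different data being collected. Which rule applies is for the investigators to decide.

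The cost is protocol and consent wording and modest staff time for a few participants per variant group. Some scores will be obtained remotely, which the protocol already accepts at follow-up. No new visit is needed, since the request falls at a scheduled time point.
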